## **10. BENEFITS**

Participants may learn self-regulation skills through the Laddr mobile application, which may have a positive impact on their smoking (in the smoking sample) or binge eating behavior (in the binge eating sample). Additionally, the information to be gained from their participation may benefit others in the future. Knowledge of brain function may have implications for our understanding of the diagnosis or treatment of CNS disease in the future.

## 11. PRIVACY AND CONFIDENTIALITY

All participant information and specimens are handled in compliance with the Health Insurance Portability and Accountability Act (HIPAA) and privacy policies of Stanford University, Stanford Health Care, and Stanford Children's Health.

Applying Novel Technologies and Methods to Inform the Ontology of Self-Regulation: Aim 4

Statistical Analysis Plan

NCT03687658

August 29, 2023

Statistical Analysis Plan (SAP)

Objective: The primary objective of the analyses is to assess changes across time in various measures in binge eaters and smokers. Specifically, we aim to determine if there is a significant effect of time (day 1 to 28 of EMA responses) on each of the outcome measures.

1. Data Management:

Raw data will be cleaned and any inconsistencies will be resolved. Any missing data will be identified and excluded.

2. Descriptive Statistics:

Generate summary statistics (mean, standard deviation, frequency, and percentages) for all outcomes of interest, stratified by day.

3.Outcome Measures:

a. Binge eaters: a23 (Loss of Control over Eating)
Question: When you ate most recently, did you lose control over your eating?
Yes (Score: 1)
No (Score: 0)

b. Binge eaters: a22 (Overeating)
Question: Since the last prompt, when you ate most recently, did you overeat?
Yes (Score: 1)
No (Score: 0)

c. Smokers: a15 (Cigarette Consumption) Question: Since the last prompt, how many cigarettes have you smoked?

4. Statistical Analysis Methods:

For a23 (Loss of Control over Eating) and a22 (Overeating): A generalized linear mixed model (GLMM) with a binomial distribution using a logit link function will be employed. This will account for the repeated measures design, where participants provide multiple responses over days. Primary Predictor: Day (representing days 1 through 28 of EMA collected responses). Random Effect: Participant ID (id).

For a15 (Cigarette Consumption): A generalized linear mixed model (GLMM) with a Poisson distribution using a log link function will be used.

Primary Predictor: Day (representing days 1 through 28 of EMA collected responses). Random Effect: Participant ID (id).

5. Hypothesis Testing:

Null Hypothesis: There is no effect of day on the outcome measure. Alternative Hypothesis: There is a significant effect of day on the outcome measure. The significance level will be set at $\alpha = 0.05$. Any p-value below this threshold will lead to rejection of the null hypothesis in favor of the alternative.

6. Assumptions and Limitations:

The models for a23 and a22 assume a binomial distribution of the outcome. The model for a15 assumes a Poisson distribution of the outcome.

7. Reporting:

Interpretation of the results will focus on the effect of day on the outcome measures. A significant effect would imply that the respective behavior changes across the time period observed.

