## **MOBILE INTERACTION PERIOD:**

Participants will be asked to complete items in response to queries using mobile ecological momentary assessment (EMA); i.e., questions/questionnaires asked at a given time point outside of a laboratory setting via a mobile device. We will assess antecedent conditions prior to health risk behavior: smoking or binge eating among our smoking and binge eating samples, respectively. These antecedent conditions include mood, companionship, location, and temptation. We will offer the resources of Laddr? (a science-based behavior change intervention delivered via an interactive, self-directed mobile platform) to individuals and assess the effect of this mobile intervention system on putative targets of self-regulatory function. Laddr will also be used to deliver the EMAs to participants. Participants will use their own smartphones.

We will ask participants to respond to EMAs and to engage with the mobile intervention for 28 consecutive days. We will prompt them four times daily to inquire about health risk behavior and ask them to complete measures of self-regulation and potentially important contexts. Please see the attachment [EMA Questions] for the list of actual questions asked.

We will send the four prompts at random times within time windows (e.g., 8–

11:30 AM, 11:30 AM-3 PM, 3-6:30 PM, 6:30-10 PM). The time windows may vary based on participants' waking hours, and we will program through the software at least an hour between prompts (e.g., if a participant receives a prompt at 11 AM, he/she cannot receive another prompt until 12 PM). We will ask them to use Laddr daily to, at a minimum, update progress toward goals and complete various activities on the application that we expect will improve their self-regulation. Participants will be recommended priority therapy guides (binge eating for the binge eating sample; smoking for the smoking sample) and can also choose to engage with other guides, such as depression, anxiety, and substance use.

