## 8. **PARTICIPANT POPULATION**

## a. Planned Enrollment

We plan to recruit a local sample of 100 subjects; because of attrition, we may need to recruit up to 125-154 individuals in order to obtain 100 complete subjects. Sample will consist of 50 smokers and 50 individuals who binge eat (BED). These are two exemplar populations that putatively involve self-regulatory dysfunction.

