Regarding privacy concerns, participants' contact information will be linked to their study data via a code. The key to this code will be available only to the research staff at Stanford, and will be secured separately from the rest of the study data that is transmitted to Fitabase. Participants will be informed of their rights to terminate their participation in the study at any time. Participants will also be informed of their rights to remove the wrist sensors if they so choose, if they do not wish to be tracked. Participants will be given a summary of the incentive structure, and will be informed how their participation will affect their final incentive payment.

All personnel that will be present for the research activities will be essential personnel in the conduct of this research. All personnel who will interact with participants at Stanford are trained in human participants research. Moreover, all staff at Small Steps Labs LLC, which owns and operates Fitabase, will receive only coded data. No directly identifiable data will be provided to Small Steps Labs LLC staff, and the key linking participant codes to identifiers will not be shared under any circumstances.

Study participants will be informed that this research is conducted with the use of Fitabase and that coded data, which will not directly identify them, will be maintained in a database owned and operated by Small Steps Labs LLC.

Protection against risks from physical activity intervention (binge eating participants only): Participants will be encouraged to set physical activity goals in line with their current health and fitness status. Participants who have concerns about increasing their physical activity will be encouraged to contact a medical professional.

Protection against risks from smoking quit attempts (smoking participants only): While participants may experience psychological discomfort from making a smoking quit attempt, this discomfort is not beyond what participants would ordinarily encounter in daily life (e.g., cravings, disappointment from a lack of success). Laddr is designed to support participants through a smoking quit attempt. Participants experiencing psychological discomfort beyond that encountered in ordinary life will be withdrawn from the study and referred to the appropriate resources.

e. Study Conclusion

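### Missed prompts are excluded with no stated assumption and no sensitivity analysis, so a Day effect on the two eating outcomes could reflect waning, lapse-related nonresponse rather than changed behaviour

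*SAP*

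**What the plan says.** The missing-data plan is one sentence in SAP section 1: "Any missing data will be identified and excluded". It does not say whether the unit of exclusion is the prompt, the day or the participant. SAP section 6 lists only the binomial and Poisson distributions as assumptions. Neither document gives a missingness assumption, an expected response rate or a sensitivity analysis.

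The models in SAP section 4 are mixed models with Day as the only named predictor and participant as the random effect: logistic for loss of control (a23) and overeating (a22), Poisson for cigarettes (a15). On interpretation, SAP section 7 says: "A significant effect would imply that the respective behavior changes across the time period observed".

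The Protocol's section on the mobile interaction period describes Laddr as "a science-based behavior change intervention delivered via an interactive, self-directed mobile platform", and adds: "Laddr will also be used to deliver the EMAs to participants". On the schedule it says: "We will prompt them four times daily to inquire about health risk behavior". Participants are to "engage with the mobile intervention for 28 consecutive days". No control arm is described.

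**The concern.** The intervention and the outcome questionnaire share one app, so disengaging from the first can also mean silence on the second. The tested term is Day, which is also the axis along which response to a long run of prompts may fall. If the prompts that go unanswered late in the period are disproportionately those that would have recorded a lapse (here, overeating or loss of control), the answered prompts drift towards looking better while behaviour stays the same. With no comparator, nothing in the design separates that drift from real change, and the reporting rule would call it behaviour change.

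**Working it through.** **1. The plan's own figure.** The Protocol's planned enrolment gives 125 to 154 recruits for 100 complete subjects. Solving N/(1 − d): 100/(1 − 0.20) = 125 and 100/(1 − 0.35) = 153.8, rounded up to 154. The plan therefore allows for about 20% to 35% attrition. These rates are back-solved, not stated. They concern participants, not prompts.

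**2. Volume of data.** 4 prompts × 28 days = 112 per participant, and 50 × 112 = 5,600 per sample.

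**3. When the slope is biased.** For a binary outcome, within a participant:

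observed odds = true odds × P(answer | lapse) / P(answer | no lapse).

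If the true odds are flat, the spurious day 28 versus day 1 odds ratio is that response ratio on day 28 divided by the ratio on day 1. A constant ratio gives exactly 1. A false decline needs the ratio to fall with day.

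**4. Size under assumed figures.** Assume a flat event rate of 0.30, a fraction r of prompts answered, and missed prompts with k times the odds of answered ones. The observed odds o solve

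r·o/(1 + o) + (1 − r)·k·o/(1 + k·o) = 0.30.

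| k | o at r = 0.90 (day 1) | o at r = 0.60 (day 28) | Spurious OR |
|---|---|---|---|
| 1 | 0.4286 | 0.4286 | 1.00 |
| 1.5 | 0.4104 | 0.3616 | 0.88 |
| 2 | 0.3970 | 0.3176 | 0.80 |
| 3 | 0.3780 | 0.2612 | 0.69 |

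At k = 2 this corresponds to about 85% response after a lapse against 92% otherwise on day 1, and 48% against 65% on day 28. If response falls only to 75%, the k = 2 figure is 0.3545/0.3970 = 0.89.

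**5. The SAP's own model.** I simulated 50 participants, 28 days and 4 prompts a day with no true Day effect, dropped missed prompts, and fitted the random-intercept logistic model by maximum likelihood with a two-sided 0.05 test (300 runs per row). Further assumptions: 25% event probability for a median participant and a random-intercept SD of 1.

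| Nonresponse | OR day 28 vs day 1 | False rejection |
|---|---|---|
| 80% response, random | 1.00 | 3.7% |
| Falling 95% to 65%, unrelated to lapse | 1.00 | 2.7% |
| Constant: 60% after lapse, 90% otherwise | 1.00 | 4.7% |
| Dropout after a reported lapse | 0.99 | 4.7% |
| Dropout at the unreported lapse | 0.98 | 7.0% |
| General decline, lapse lowers logit of response by 0.5 | 0.87 | 18% |
| General decline, lapse lowers it by 1.0 | 0.72 | 66% |
| After lapse 90% to 80%; otherwise 90% | 0.88 | 21% |
| After lapse 90% to 70%; otherwise 90% | 0.77 | 57% |
| After lapse 90% to 60%; otherwise 90% | 0.67 | 92% |

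The last three rows agree with step 3: 0.8/0.9 = 0.89, 0.7/0.9 = 0.78 and 0.6/0.9 = 0.67. Monte Carlo error at a true 5% is √(0.05 × 0.95/300) = 1.3 points, so 7.0% is compatible with 5%. In the five rows where the lapse gap widens with day, every rejection was a decline.

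**6. Cigarette counts.** Item a15 asks for cigarettes since the preceding prompt, which can be read in two ways.
- Since the last prompt sent: cigarettes in missed windows are lost. With a missed-window mean 2 times the answered one, the spurious rate ratio is (0.9 + 0.1 × 2)/(0.6 + 0.4 × 2) = 1.1/1.4 = 0.79.
- Since the last prompt answered: cigarettes are carried forward, so the mean per answered prompt is the true mean divided by r. The ratio is 0.9/0.6 = 1.5 whatever the multiplier, an apparent worsening. Simulation gave about 1.51.

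The two eating items ask about the most recent eating occasion, so they do not accumulate in this way.

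**The case against.** The strongest defence is that a likelihood-fitted mixed model using all answered prompts is valid under MAR. That stands: the simulation shows error near 5% when missingness is random or follows a reported lapse. What remains is that the SAP neither states the assumption nor tests departures from it.

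Second, the Protocol pays for response: $0.50 per prompt and $10 a week for at least 25 of 28 (89%), separately from the payment for Laddr activities. A participant can therefore ignore the therapy content and still answer. This may keep response high and the bias small, but it is not an analysis rule and does not show that the remaining nonresponse is ignorable.

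Third, SAP section 2 asks for frequencies by day, which could reveal a fall in answered prompts. It could not reveal the cause.

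A reader might go further in three ways that the documents do not support:
- That a lapse which makes someone stop using the app is enough to create a false trend. Dropout at the unreported lapse gave an odds ratio of only 0.98.
- That smokers would show a false decline. The wording of a15 allows the opposite sign.
- That the Protocol's rule on withdrawing participants for discomfort beyond ordinary life documents lapse-driven missed prompts. It is a safety provision tied to quit attempts, and it counts cravings and disappointment at lack of success as ordinary.

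**Conclusion.** The gap is real and conditional. For a22 and a23, a false decline arises if response wanes over the 28 days and is also lower after a lapse, so that the response ratio falls with day. This is plausible when one app carries both treatment and measurement, but the documents do not show that it happens. Under the assumed 30% event rate and 90% to 60% response, the spurious odds ratio is 0.88 to 0.69 for multipliers of 1.5 to 3. No response rate is given, so the true size is unknown and may be negligible. For a15 the sign itself is open. The SAP's test is non-directional; a decline is simply the direction that this mechanism would give for the eating outcomes. The planned analysis need not be replaced. What is unsupported is reading a significant Day effect as behaviour change without a test of its dependence on the missed prompts.

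**What to change.** Amend the SAP as follows.

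1. Keep the mixed models as primary, fitted to every answered prompt. State that exclusion is at prompt level, that no participant is dropped for incomplete data, and that the analysis assumes MAR.
2. Tabulate the number and percentage of prompts answered by day, for each sample.
3. Add a delta-adjusted multiple-imputation tipping-point analysis for missed prompts: impute from the fitted model, multiply the odds (or the rate, for a15) by values such as 1, 1.5, 2 and 3, refit and pool. If the estimated trend is upward, use the reciprocals. Run a15 under both readings of the recall window.
4. Change the reporting section so that a significant Day effect is described as behaviour change only together with the multiplier at which it loses significance.

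Adding each participant's proportion of answered prompts and its interaction with Day is not an adequate substitute. With a decline in response common to all participants (200 simulated data sets), that interaction was significant in 6.5% and 7.5% of runs at multipliers of 2 and 3, while Day was falsely significant in 43% and 78%. It could reassure wrongly.

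The cost is SAP wording and some additional model fits, with no new data collection. The downside is that the Day effect may look less secure.

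### The Day effect on cigarette counts (a15) could partly reflect prompt compliance, and the SAP plans no analysis that would show whether it does

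*SAP*

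**What the plan says.** SAP section 3c defines a15 by the question "Since the last prompt, how many cigarettes have you smoked". For its model, section 4 says "A generalized linear mixed model (GLMM) with a Poisson distribution using a log link function will be used", with "Primary Predictor: Day (representing days 1 through 28 of EMA collected responses") and a participant random effect. No other predictor, exposure term or prompt-window term is named. Section 1 says "Any missing data will be identified and excluded".

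The SAP does not say which prompt an answer counts from when the one before it was missed, or what the first prompt of day 1 covers. It does not state for a15 whether a row is one response or a daily total. The nearest text, "This will account for the repeated measures design, where participants provide multiple responses over days", is written for a22 and a23; it points to one row per response.

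Section 7 gives the reading of the result: "A significant effect would imply that the respective behavior changes across the time period observed".

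The protocol (section 2, Mobile Interaction Period) sends four prompts a day at random times within windows. It speaks of prompts as sent and received: "if a participant receives a prompt at 11 AM, he/she cannot receive another prompt until 12 PM". It adds that "The time windows may vary based on participants' waking hours". It refers to an attachment for the EMA questions, which was not available for this review.

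**The concern.** A Poisson count needs a known exposure. Here the exposure is the time back to a previous prompt. If that prompt was missed, a smoker may count from when it was delivered or from the last one answered. Under the second reading a miss lengthens the period the next answer covers. If misses become more common over the 28 days, the average count rises although smoking has not changed, and Day absorbs the rise.

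Testing Day is the SAP's stated primary objective, and a15 is its only smoking outcome. Smokers are given a goal of abstinence by the end of the study (protocol, Mobile Interaction Period), so a fall is hoped for. On per-response rows, falling compliance would shrink a real fall or create a false rise; rising compliance would do the opposite. Section 7 as written would read either as behaviour.

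**Working it through.** The documents give no effect size, expected compliance or power for a15, so there is no planned figure to reproduce.

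**Inputs from the documents.** 50 smokers (protocol 8a). 4 prompts × 28 days = 112 prompts each. Example windows of 3.5 hours from 8 AM to 10 PM, at least one hour between prompts. Weekly bonus at 25 of 28 prompts = 89.3% (protocol 8k), so some misses are foreseen.

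**Assumptions.** 10 cigarettes a day (entry requires 5 or more), the compliance paths, and the share f of smokers who count from the last answered prompt. Misses are unrelated to smoking unless stated.

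**1. Look-back bias.** If each prompt is answered with probability p, the mean distance back to the last answered prompt is 1/p intervals. With no true change the false ratio is

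R = [(1 − f) + f/p28] / [(1 − f) + f/p1].

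For 90% to 70%: f = 0.25 gives (0.75 + 0.357)/(0.75 + 0.278) = 1.107/1.028 = 1.08; f = 0.5 gives 1.214/1.056 = 1.15.

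| Compliance, day 1 to 28 | f = 0 | 0.25 | 0.5 | 1 |
|---|---|---|---|---|
| 90% to 90% | 1.00 | 1.00 | 1.00 | 1.00 |
| 90% to 80% | 1.00 | 1.03 | 1.07 | 1.13 |
| 90% to 70% | 1.00 | 1.08 | 1.15 | 1.29 |
| 90% to 60% | 1.00 | 1.14 | 1.26 | 1.50 |

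Simulating the prompt schedule (400 runs per setting, Poisson on Day conditional on participant) gave 1.00, 1.07, 1.15 and 1.29 for the 90% to 70% row. A random-intercept Poisson GLMM agreed with the conditional fit within 0.0004 in 20 check fits. Compliance rising from 80% to 90% with f = 1 gives 0.8/0.9 = 0.89.

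**2. Effect on a real fall.** Multiply by R. A true ratio of 0.80 at 90% to 70% becomes about 0.86 (f = 0.25) or 0.92 (f = 0.5). A true 0.50 becomes about 0.54 or 0.58: shrunk, not hidden.

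**3. Effect on the test.** With no true change, day-to-day rate CV 0.5 and participant-clustered standard errors, simulated rejection was 3% at constant 90% with f = 0. At 90% to 70% it was 18% for f = 0.25 and 60% for f = 0.5.

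**4. Drift in one window (f = 0).** If smokers are awake 7:00 to 23:00, the morning answer covers on average 5.5 waking hours and the other three 3.5. If only morning compliance falls, 90% to 50%:

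[(0.5 × 5.5 + 2.7 × 3.5)/3.2] / [(0.9 × 5.5 + 2.7 × 3.5)/3.6] = 3.81/4.00 = 0.95.

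A window effect returns this to 1.00. It does not cure step 1: with f = 0.25 and 90% to 70%, the ratio with a window effect was still 1.075.

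**5. First prompt of day 1.** The leverage of day 1 on the log ratio is 27 × (−13.5)/1827 = −0.1995. If that answer covers 24 hours (10 cigarettes instead of 2.5), day 1 is 0.75 too high and the ratio is exp(−0.1995 × 0.75) = 0.86. If it covers only the time since 8 AM, day 1 is 0.125 too low and the ratio is exp(0.1995 × 0.125) = 1.03. Neither needs any drift.

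**6. Unit of analysis.** With daily sums and counting from the last delivered prompt, 90% to 70% gives 0.7/0.9 = 0.78, so the bias reverses.

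**7. Filtered rows.** Where the preceding prompt was answered, last delivered and last answered are the same prompt. With this filter and a window effect, simulated ratios were 0.996 to 1.002 under no true change at every drift and share tried. With day-level CV 0.5, rejection was about 30% on the SAP's Poisson standard errors and 5 to 8% on clustered ones.

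**The case against.** The strongest reply is that the plan's own words remove the main bias. The question refers to a prompt, not an answer, and the protocol describes prompts as sent and received. On that reading f = 0 and step 1 gives 1.00 at every level of uniform drift. The bias needs drifting compliance and last-answered counting together, and the documents show neither. Payment is even over the four weeks, and 25 of 28 is a bonus threshold, not a forecast. The EMA attachment may settle the look-back and the first prompt. All of this stands, and it is why the point is conditional.

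What it does not remove is window-specific drift, the first prompt of day 1 and the unstated unit, none of which depends on f. Nor does the wording show how participants counted. If the attachment defines the look-back, the SAP model still has to match it.

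A reader might infer that the planned Day effect is biased, or that falling compliance would produce a false success. The documents support neither. There are no compliance data, and on per-response rows falling compliance with last-answered counting works against finding a fall. A false fall needs rising compliance, daily sums or one of the special cases in steps 4 and 5.

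It is also fair that the daily breath CO reading has no look-back problem. The SAP does not analyse it, so it does not serve as a check at present.

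**Conclusion.** The point holds in conditional form, as a worthwhile and inexpensive improvement to the plan. With stable compliance, or with all smokers counting from the last delivered prompt, the per-response slope is about right apart from steps 4 and 5. With compliance falling from 90% to 70% and a quarter to a half of smokers counting from the last answered prompt, the false ratio is about 1.08 to 1.15. The drift, the shares, the smoking rate and the waking hours are all assumed, and the plausible range includes 1.00. Confidence is medium, because compliance by day and the EMA attachment would decide how much of this applies.

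Overdispersion of the counts is a separate matter. It enters here only because the remedy needs standard errors that allow for it.

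**What to change.** Keep the all-answers model as primary, and amend SAP sections 3c, 4 and 7 as follows.

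1. State that a15 is analysed per response, not as a daily total.
2. Leave out the first prompt of day 1, which has no predecessor.
3. Add a fixed effect for prompt window.
4. Pre-specify a sensitivity analysis limited to answers whose immediately preceding prompt was also answered, with the window effect and participant-clustered (or otherwise overdispersion-robust) standard errors.
5. Tabulate compliance by day and window.
6. Report both estimates with intervals. Where they differ and compliance drifts, do not read the all-answers Day effect alone as behaviour change.

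Two tempting additions should be avoided. Requiring both analyses to be significant in the same direction would discard correct findings: with a true ratio of 0.80 and falling compliance, the filtered analysis detected the fall in 86 to 95% of simulated runs, but the joint rule passed in only 0 to 16%. An offset for waking hours is not workable, because the documents describe no wake-time record for smokers.

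**Cost.** SAP wording, one factor, one row filter and one table. Answered or missed status should already be held, since protocol 8k pays per EMA. The planned end was August 2022 (protocol 8m) and the SAP is dated August 2023, so the question can probably no longer be changed, but none of these steps needs new data. If a15 has already been analysed, label the added analysis as such.

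The window effect adds under 1% to the standard error, and leaving out the day-1 prompt 1 to 3%. The filtered standard error is about 5 to 13% larger at 90% compliance. As a rough check, the filter keeps 90% of answered rows, and 1/√0.9 = 1.05; if all count from the last answered prompt it keeps 81% of the cigarettes counted, and 1/√0.81 = 1.11. The cost rises at lower compliance, to 46% at a constant 70% with all counting that way.

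The filter is not a full cure if misses depend on smoking. With the log-odds of answering falling 0.2 per cigarette and compliance 90% to 70%, it gave 0.95 under no true change, against 0.94, 1.15 and 1.33 for the all-answers model (f = 0, 0.5 and 1).

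### The participant random effect does not cover dependence among up to four same-day answers, so the Day test for a23 and a22 can exceed its stated 5%

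*SAP*

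**What the plan says.** SAP section 4 fits a23 (loss of control) and a22 (overeating) by a binomial logit mixed model. The tested term is given as "Primary Predictor: Day (representing days 1 through 28 of EMA collected responses", and the clustering is specified as "Random Effect: Participant ID (id". The SAP then states of this model: "This will account for the repeated measures design, where participants provide multiple responses over days". Section 6 lists only the binomial assumption. Neither document names a day-level term, a serial correlation or a robust variance, or says whether Day enters as a linear trend or as a factor.

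On the data, the protocol (Mobile Interaction Period) says "We will prompt them four times daily to inquire about health risk behavior", at random times within windows, and "we will program through the software at least an hour between prompts". Over 28 days this gives up to 4 x 28 = 112 answers per person.

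In SAP section 3, a22 is limited to eating after the previous prompt. The printed a23 has no such limit: "When you ate most recently, did you lose control over your eating".

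Section 5 tests each outcome without a stated direction: "Alternative Hypothesis: There is a significant effect of day on the outcome measure". "The significance level will be set at" 0.05. Section 7 reads a significant Day effect as a change in behavior.

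**The concern.** A participant intercept absorbs stable differences between people. It does not absorb what the answers of one person on one day have in common. Two sources of such dependence are plausible here.

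- **Same-day correlation (a22 and a23).** The protocol's EMA items include mood, companionship, location and temptation. If such conditions persist through a day, they move all of that day's answers together.
- **Repeated occasions (a23 only, as printed).** A participant who has not eaten between two prompts would report the same meal twice, and the model counts two independent outcomes.

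Because Day is constant within a day, positive dependence of either kind feeds straight into the variance of the Day coefficient. The model-based standard error is then too small, the confidence interval too narrow and the p-value too low. The Day effect is the SAP's whole stated objective, so an understated standard error could turn day-to-day clustering into a reported change in eating behavior. This needs no difference in trend between people.

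**Working it through.** **Inputs from the documents:** alpha 0.05, taken as two-sided because the alternative has no direction (SAP 5); participant-only random effect (SAP 4); 28 days (SAP 4); four prompts a day, at least one hour apart, with 3.5-hour example windows (protocol, Mobile Interaction Period); 50 binge eating participants (protocol 8a).

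**Assumptions, not in the documents:** linear Day; participant SD 1.0 on the logit; 30% Yes for a participant at the average; all prompts answered unless stated; q = share of the day's second to fourth prompts that repeat the previous answer; s = day-level SD on the logit.

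**Step 1. Reproduce the 5%.** With a design effect (deff) of 1, rejection is 2 x (1 - Phi(1.96)) = 0.050. The SAP's model, fitted by quadrature to 3,000 simulated trials with independent answers and no Day effect, rejects 4.7%. Sharing a Day value does no harm by itself.

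**Step 2. Repeated occasions (a23).** Since Day is constant within a day,

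deff = 1 + 2 x [(3/4)q + (2/4)q^2 + (1/4)q^3], and rejection = 2 x (1 - Phi(1.96/sqrt(deff))).

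For q = 0.2: deff = 1 + 2 x (0.150 + 0.020 + 0.002) = 1.344, and rejection = 2 x (1 - Phi(1.69)) = 9.1%.

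| q | deff | formula | simulated (3,000 runs) |
|---|---|---|---|
| 0.1 | 1.161 | 6.9% | 7.4% |
| 0.2 | 1.344 | 9.1% | 9.1% |
| 0.3 | 1.553 | 11.6% | 12.7% |
| 0.4 | 1.792 | 14.3% | 14.3% |

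Monte Carlo SE is about 0.4-0.6 points. Variants at q = 0.2: 8.1% with 75% of prompts answered, 12.2% if repeats also cross midnight, 8.9% with about 10% Yes, and 8.7% with 25 participants.

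**Step 3. What q might be.** Prompt times were drawn from the protocol's example windows (mean gap about 3.5 hours). The chance of no eating between consecutive prompts is 0.17-0.39 for four to eight randomly timed occasions per 14 hours, and 0.12-0.36 for three to six regularly timed ones. Both eating patterns are assumptions.

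**Step 4. Day-level effect without repeats (a22, and a23).** Simulated rejection is 5.5% at s = 0.25, 6.6% at 0.5, 9.4% at 0.75 and 10.6% at 1.0. As a cross-check, an exchangeable within-day correlation rho gives deff = 1 + 3 x rho. At rho = 0.10 this is 1.30, with rejection 8.6%.

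**Step 5. Remedies.**

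- Participant-clustered (sandwich) variance with t on N-1 df: 4.3-6.4% in every scenario of steps 1, 2 and 4. At q = 0.2 it gives 5.3%, at q = 0.3 it gives 4.8%.
- Participant-by-day random intercept: 4.5-5.0% in separate simulations (2,000 runs per scenario, 80% of prompts answered) covering no dependence, q of 0.15, 0.25 and 0.34, s = 0.7, and q = 0.25 with s = 0.5.
- Random Day slope alone: 4.3-6.0% in runs of 600 per scenario (SE about 1 point).
- Limit of the day intercept alone: in a daily-level linear approximation with an assumed between-person slope SD of 0.02 or 0.03 logit per day, it still rejects about 9% or 15%.

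The day intercept and random slope were not simulated together.

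**The case against.** The strongest reply is that the size of the problem rests on quantities the documents do not supply. That is right: no repeat share, within-day correlation, outcome rate or compliance rate is given. A reader might infer that the a23 test is known to reject at some fixed rate such as 8-13%. The documents do not support that, because such a band follows only if roughly 15-35% of prompts repeat an occasion.

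The repeat mechanism is also unconfirmed. The protocol refers to an attachment for the EMA items. By its number a23 follows a22, so it may share a22's time limit or be skipped when nothing was eaten. Repeats would then drop out, leaving only ordinary same-day correlation. The one-hour gap is a minimum; most gaps would be longer.

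For a22 the upper a23 figures do not apply, and a modest day-level SD of 0.25-0.5 gives only 5.5-6.6%. An SD of 1.0 would make day-to-day swings as large as the simulated differences between people.

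Two stronger readings also fail. Several answers sharing one Day value is not itself a fault, as the 4.7% in step 1 shows. Nor is the SAP's sentence simply false: the intercept does handle stable differences between participants.

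What stands is the direction. Positive within-day dependence inflates the Day test, and nothing in the plan guards against it.

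**Conclusion.** The point holds conditionally. The SAP's statement about repeated measures is incomplete, and the Day test for a23 and a22 exceeds 5% to the extent that same-day answers correlate or repeat. With a linear Day term, the excess runs from negligible to nearly threefold: about 7-14% for a23 at repeat shares of 0.1-0.4, and about 5.5-10.6% for a22 (and for a23 without repeats) at day-level SDs of 0.25-1.0. These are results under assumed inputs, not estimates for this trial, and larger dependence would give larger figures. If Day were fitted as a 27-df factor the inflation would be much greater (about 32% at q = 0.2 by the analogous formula). The correction is cheap and the Day test carries the whole conclusion, so the change should be made.

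**What to change.** In SAP section 4, for a23 and a22, name one of these as the basis of the section 5 Day test:

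1. the planned model with a participant-clustered (sandwich) variance and a t reference on N-1 df; or
2. the planned model with a participant-by-day random intercept together with a random Day slope by participant. The day intercept alone handles within-day dependence but not differing trends between people.

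Replace the sentence on repeated measures with one saying which dependence each term covers, and state whether Day is linear. If the EMA data identify new eating occasions, a supporting a23 analysis using only the first answer per occasion can be added; the documents do not show that such an item exists, so this is optional.

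The cost is SAP wording and slightly more analysis work, with no new data. The interval for Day widens according to the dependence present: by the step 2 formula, about 8% at q = 0.1 (sqrt(1.161) = 1.08) and 34% at q = 0.4 (sqrt(1.792) = 1.34).
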